2.2.1 Hospital admissions due to any cause

2.2.2 Hospital admissions excluding those due to external causes or surgery

2.2.3 **Hospital admissions due to malaria.** Defined as hospital admissions where malaria was the primary diagnosis, supported by a positive blood smear, or positive RDT if no blood smear result was available. Additional analyses of children who meet the WHO criteria for a diagnosis of severe malaria including those with a) cerebral malaria, b) severe anaemia and c) other forms of severe malaria will be undertaken.

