2.5 Other secondary outcomes

2.5.1 The prevalence of molecular markers of resistance to SP and AQ in children with *P. falciparum* infection, among samples collected at the final cross-sectional survey in December 2019. These include the dhfr 51-59-108 triple mutation, dhps-A437G, and dhps-K540E mutations for resistance to SP, and the pfcr1 K76T and pfmdr1 N86Y mutations for resistance to AQ.

2.5.2 The percentage of children with asymptomatic *P. falciparum* parasitaemia at the cross-sectional survey in December 2019, who, when treated with SP+AQ, have an adequate clinical and parasitological response (ACPR) after 28 days.

Serious Adverse Events

In addition to the comparison of incidence rates described above (section 2.2), serious adverse events (SAEs) defined as hospitalisations or death, occurring at any time during the study will be tabulated by study group according to their cause.

Safety signals from the RTS,S/AS01 phase 3 studies

The incidence of meningitis has been very low in the study cohort, with no events up to the 30th November 2019. A 95% confidence interval for the incidence rate of meningitis among children vaccinated with RTS,S/AS01 will be calculated.

The incidence of cerebral malaria among children vaccinated with RTS,S/AS01 will be investigated by comparing the RTS,S/AS01 groups with the SMC alone group, controlling for SMC status using an indicator variable. Cox regression will be used to obtain the hazard ratio and its 95% confidence interval.

The incidence of febrile convulsions not related to malaria or another obvious cause among children vaccinated with RTS,S/AS01 will be investigated as for cerebral malaria, i.e. by comparing the RTS,S groups with the SMC alone group, controlling for SMC status using an indicator variable. Cox regression will be used to obtain the hazard ratio and its 95% confidence interval. The subset of febrile convulsions that occurred within 7 days of vaccination will also be analysed.

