- the actual timing of SMC cycle 1 in relation to the malaria transmission season;
- the mean and range of the intervals between the monthly SMC courses;
- the adherence to daily doses of SMC each month

Separate profiles will be produced for each of the two trial centres.

Statistical methods

Reference group

As SMC is the current standard of care, the SMC alone group will be considered as the reference group for comparisons with RTS,S/AS01 alone, and the combined group. Comparisons will also be made between RTS,S/AS01 alone and the combined group.

Primary endpoint

The hazard ratio for the primary outcome will be estimated using Cox regression models, with a robust standard error (i.e. the Andersen-Gill extension of the Cox model) to account for potential clustering of episodes within children. The Efron method will be used for tied event times.

The timescale will be calendar time, starting from 1st April 2017, i.e. allowing delayed entry according to the precise timing of the first vaccination contact. This ensures that risk sets in the Cox models are comparable with respect to the timing of onset of transmission each year, and the timing of SMC. Due to variable timing in vaccine dose 1 in 2017, this would not be the case if the data were analysed on the time in study timescale.

Nelson-Aalen Cumulative hazards will be plotted for each group to show the mean number of events per child during the study and the timing of events, and Kaplan Meier failure estimates will be plotted to show the risks during the study.

As recommended in the updated CONSORT guidelines (8), the incidence rate differences (IRD) will also be calculated, as this gives an indication of the reduction in incidence attributable to the interventions, i.e. the absolute public health impact in similar contexts. The IRD will be calculated using ordinary least squares regression of transformed variables, as described by Xu et al. (9). This method uses a robust standard error and controls for unequal follow-up time, as well as quantitative or multiple covariates. To aid interpretation, the risk of the primary outcome will also be estimated from the Kaplan-Meier estimate of the risk.

Secondary endpoints

Secondary outcomes which are passively detected events, will be analysed in a similar way as for the primary outcome, i.e. estimating the hazard ratio using Cox regression with a robust standard error.

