SMC	2000	6000.0	1333	180.0 (120.0, 240.0)	(Reference)		P=0.0	P=0.0
RTS,S	2000	6000.0	1333	180.0 (120.0, 240.0)	1.00 (0.90, 1.10)	Reference		
Combined	2000	6000.0	1333	180.0 (120.0, 240.0)	1.00 (0.90, 1.10)	1.00 (0.90, 1.10)		
Total	6000	18000.0	4000	180.0 (120.0, 240.0)	-	-	-	
Mali								
SMC	2000	6000.0	1333	180.0 (120.0, 240.0)	(Reference)		P=0.0	
RTS,S	2000	6000.0	1333	180.0 (120.0, 240.0)	1.00 (0.90, 1.10)	Reference		
Combined	2000	6000.0	1333	180.0 (120.0, 240.0)	1.00 (0.90, 1.10)	1.00 (0.90, 1.10)		
Total	6000	18000.0	4000	180.0 (120.0, 240.0)	-	-	-	

Numbers are included only to give an idea of layout / spacing.

Table 2: Incidence of the primary outcome by study year: number of cases of clinical malaria; person-years at risk (PYAR); rates per 1000 person-years; and P-values from tests of homogeneity among all study children. The results of the test of interaction by study year will also be shown.

	No. children	PYAR	No. events	Rate/1000 (95% CI)	Rate Ratio (95% CI)		Test of homogeneity ¹	Interaction by Year
Study Year 1								
SMC	2000	6000.0	1333	180.0 (120.0, 240.0)	(Reference)		P=0.0	
RTS,S	2000	6000.0	1333	180.0 (120.0, 240.0)	1.00 (0.90, 1.10)	Reference		
Combined	2000	6000.0	1333	180.0 (120.0, 240.0)	1.00 (0.90, 1.10)	1.00 (0.90, 1.10)		
Total	6000	18000.0	4000	180.0 (120.0, 240.0)	-	-	-	
Study Year 2								
SMC	2000	6000.0	1333	180.0 (120.0, 240.0)	(Reference)		P=0.0	P=0.0
RTS,S	2000	6000.0	1333	180.0 (120.0, 240.0)	1.00 (0.90, 1.10)	Reference		
Combined	2000	6000.0	1333	180.0 (120.0, 240.0)	1.00 (0.90, 1.10)	1.00 (0.90, 1.10)		
Total	6000	18000.0	4000	180.0 (120.0, 240.0)	-	-	-	
Study Year 3								
SMC	2000	6000.0	1333	180.0 (120.0, 240.0)	(Reference)		P=0.0	
RTS,S	2000	6000.0	1333	180.0 (120.0, 240.0)	1.00 (0.90, 1.10)	Reference		
Combined	2000	6000.0	1333	180.0 (120.0, 240.0)	1.00 (0.90, 1.10)	1.00 (0.90, 1.10)		
Total	6000	18000.0	4000	180.0 (120.0, 240.0)	-	-	-	

Numbers are included only to give an idea of layout / spacing.

Similar tables will be used to report the incidence of passively detected secondary outcomes.

Table 3: Prevalence of *P. falciparum* infection at the end of malaria transmission season surveys: number of children tested; number with the outcome of interest; prevalence (95% CI); prevalence ratio (95% CI) and P-values from tests of homogeneity will be shown.

	No. children with result	No. with outcome	Prevalence (95% CI)	Prevalence Ratios (95% CI)		Test of homogeneity ¹
P. falciparum infection						

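### With SMC coded by allocated arm, the RTS,S hazard ratio for cerebral malaria and febrile convulsions is Combined versus SMC-alone, not both RTS,S groups versus SMC-alone as the SAP states

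*Combined protocol and SAP*

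**What the plan says.** The section of SAP revision 1 on safety signals from the phase 3 studies plans one Cox hazard ratio for cerebral malaria, "comparing the RTS,S/AS01 groups with the SMC alone group, controlling for SMC status using an indicator variable". It plans another for febrile convulsions without malaria or another obvious cause, "by comparing the RTS,S groups with the SMC alone group, controlling for SMC status using an indicator variable". It then adds: "The subset of febrile convulsions that occurred within 7 days of vaccination will also be analysed". SMC status is not defined there. The exploratory sex-by-mortality model that follows adjusts for SMC receipt, also without a definition. Under *Analysis populations*, children stay in the modified intention-to-treat population whatever later doses they received, and all secondary outcomes use that population.

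Other parts of the SAP bear on the same outcomes:

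- Section 2.2.3 plans "Additional analyses of children who meet the WHO criteria for a diagnosis of severe malaria including those with a) cerebral malaria".
- *Statistical methods* says "Secondary outcomes which are passively detected events, will be analysed in a similar way as for the primary outcome", and that "the SMC alone group will be considered as the reference group for comparisons with RTS,S/AS01 alone, and the combined group", with RTS,S-alone also compared with Combined.
- The planned incidence tables carry the pairwise ratios, and "Similar tables will be used to report the incidence of passively detected secondary outcomes".
- Serious adverse events, defined as hospitalisations or deaths, "will be tabulated by study group according to their cause".

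Febrile convulsions are not a numbered endpoint.

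**The concern.** The wording promises a comparison that includes every RTS,S recipient. The trial has three of the four cells of a two-by-two factorial, so adjusting for SMC leaves only one pair of arms that differ in RTS,S while sharing SMC status: Combined and SMC-alone. A reader of the safety table would take the hazard ratio to cover about two thirds of the randomised children as vaccinees, when the RTS,S-alone half of them has almost no influence on it.

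For cerebral malaria the pairwise contrasts appear to be planned elsewhere. For convulsions, the paragraph commits to no reported hazard ratio in which the RTS,S-alone arm counts. The 7-day subset is where this costs something: it is the analysis closest to vaccine reactogenicity, and half the vaccinated children would drop out of the contrast in order to adjust for a drug not yet given that season.

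**Working it through.** **Inputs.** The SAP gives no figure for these analyses, so there is nothing to reproduce. The arm definitions come from *Study groups*, the dates from *Precise timing of interventions*, and the model from the safety-signals section. Event counts below are assumptions.

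**1. What the coefficient estimates.** Code each arm as (R, S) for RTS,S and SMC by allocation. The log hazard relative to the (unobserved) neither-intervention level is:

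| Arm | R | S | Log hazard |
|---|---|---|---|
| SMC-alone | 0 | 1 | bS |
| RTS,S-alone | 1 | 0 | bR |
| Combined | 1 | 1 | bR + bS |

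Therefore:

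- Combined minus SMC-alone = bR
- Combined minus RTS,S-alone = bS
- RTS,S-alone minus SMC-alone = bR - bS

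The design with an intercept has rank 3 for three arms. Its inverse gives bR weights of (-1, 0, +1) on the SMC-alone, RTS,S-alone and Combined log rates, and gives bS weights of (0, -1, +1). The difference bR - bS has weights (-1, +1, 0).

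**2. Numerical illustration.** Assume equal follow-up and 10, 20 and 10 events in SMC-alone, RTS,S-alone and Combined.

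- RTS,S hazard ratio from the model: 10/10 = 1.00. The standard error is sqrt(1/10 + 1/10) = 0.447, so the 95% CI is exp(±1.96 × 0.447) = 0.42 to 2.40. It is the same if RTS,S-alone has 5, 10 or 40 events.
- RTS,S-alone versus SMC-alone from the same fit: 20/10 = 2.00. The standard error is sqrt(1/20 + 1/10) = 0.387, so the 95% CI is 0.94 to 4.27.

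**3. Does Cox behave the same way?** The identity is exact for arm-level Poisson rates. In Cox, the RTS,S-alone arm can enter only through shared risk sets and the country coefficient. In simulated trials (2,000 children per arm, Efron ties, country-adjusted) averaging about 62, 340 and 63 events, the SMC-adjusted RTS,S hazard ratio was 1.015. A fit to Combined and SMC-alone only also gave 1.015. The unadjusted pooled ratio was 3.39. Across scenarios, the adjusted and two-arm log hazard ratios differed by 0.001 to 0.005 on average. The largest difference was 0.025, in the scenario with about 6 events in each of SMC-alone and Combined, where the standard error was 0.63.

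**4. The 7-day subset: timing.** In 2017 the third dose was given between late June and early July, and the first SMC course began in late July. In 2018 and 2019 the booster was given in the first two weeks of June, and SMC began in the second week of July. So three of the five scheduled doses precede any trial SMC, and the other two precede that season's SMC.

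**5. The 7-day subset: precision.** Assume e events in each RTS,S arm and e/HR in SMC-alone, with equal person-time.

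- Variance of log HR, SMC-adjusted: 1/e + HR/e = (1 + HR)/e
- Variance of log HR, pooled: 1/(2e) + HR/e = (0.5 + HR)/e

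| HR | Adjusted × e | Pooled × e | Reduction |
|---|---|---|---|
| 1 | 2.0 | 1.5 | 25% |
| 2 | 3.0 | 2.5 | 17% |
| 3 | 4.0 | 3.5 | 12.5% |

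Two-sided 5% Wald power at HR 2 rises from 43% to 50% with e = 20, from 24% to 28% with e = 10, and from 15% to 17% with e = 5.

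**The case against.** The strongest defence is that the adjusted model is the right one for the question. With no arm lacking both interventions, Combined versus SMC-alone is the only pair that isolates the vaccine. An unadjusted whole-period pool would mix in the effect of withholding SMC. This stands: a reader might infer that the planned hazard ratio is invalid or confounded, and it is neither. The fault lies in how it is described.

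Three further readings are tempting and go too far.

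- *That SMC status might mean time-updated receipt, so the estimand is open.* The term is undefined, but nothing in this section proposes split SMC person-time. The SAP names Lexis expansion where it wants person-time split, and modified intention to treat points to allocated arm.
- *That the RTS,S-alone arm is left out of the modelling.* The fit is saturated and contains RTS,S-alone versus SMC-alone as bR - bS. The general *Reference group* rule could also be read as covering convulsions. What is missing is a clear commitment: the convulsion paragraph sets its own single comparison, and convulsions are not a numbered endpoint to which the planned tables plainly apply.
- *That the 7-day subset has no model.* The sentence directly follows the Cox specification and naturally inherits it. The question is whether the inherited SMC term suits that window.

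Nor would an RTS,S-alone excess in a malaria outcome by itself be a vaccine signal, because that arm goes without SMC.

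It can also be said that the precision gain is small and that pooling gives up adjustment for earlier seasons' SMC. Both are true, which is why the adjusted estimate should be shown beside the pooled one.

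**Conclusion.** The concern holds as a mismatch between the stated comparison and what the model delivers. Under allocated-arm coding, the cerebral malaria and convulsion hazard ratios are essentially Combined versus SMC-alone. Extending them to all RTS,S recipients assumes no interaction between RTS,S and SMC, which this design cannot test. For cerebral malaria the consequence is a label and a cross-reference. For convulsions it is also an unreported contrast that the model already contains.

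For the 7-day subset, the SMC term sets aside the RTS,S-alone arm for little or no control of confounding. The variance cost is about 25% at the null and 17% at a hazard ratio of 2, if both RTS,S arms have the same number of events. The power figures rest on assumed counts. The timing argument applies to scheduled doses; the per-protocol text shows that some catch-up vaccination was attempted later in the season. Severity is minor.

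**What to change.** 1. State that SMC status means allocated arm. Label the modelled hazard ratio *Combined versus SMC-alone (RTS,S effect given SMC)*.
2. For convulsions over the whole period, also report RTS,S-alone versus SMC-alone from the same model (bR - bS with its 95% CI), labelled as vaccine given and SMC withheld. For cerebral malaria, cross-refer to the pairwise contrasts under section 2.2.3 and say that they cover it.
3. For convulsions within 7 days of vaccination, specify a country-adjusted Cox model pooling both RTS,S arms against SMC-alone, and report the SMC-adjusted estimate beside it.

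The cost is SAP wording and a few lines of code, with no new data. The drawback is that the pooled 7-day estimate does not adjust for earlier-season SMC, in which the arms differ by the 2018 and 2019 doses; the adjusted estimate alongside lets the reader judge whether that matters.

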3 STUDY AREA

The trial will be conducted in Houndé health district, Burkina Faso and in Bougouni Koulikoro district, Mali. The Houndé district is situated 300 km from Ouagadougou and 100 Km from Bobo-Dioulasso where the CHUSS, the 2nd National Reference Hospital (University Hospital), is located and which is also a base of the IRSS. The study site in Mali is the district of Bougouni in the region of Sikasso, Mali, 150 km south of Bamako where the MRTC is based.

Figure 1 : Map of Mali and Burkina Faso showing the two sites.

The population of Houndé district belongs primarily to the Bwaba ethnic group and that of Bougouni primarily to the Bambara and Fula ethnic groups. Farming is the main occupation in each area. Each district has a district hospital.

Malaria, due predominantly to *Plasmodium falciparum*, is highly seasonal in both districts with over 80% of cases occurring during the rainy season (July – October) and during the following month. The prevalence of *P. falciparum* malaria in school age children in December 2015 was 53% in Bougouni and 62% in Houndé. The main malaria vector in each study area is *Anopheles gambiae* ss. A high proportion of children sleep under an ITN in Bougouni (96%) but the percentage is less in Houndé. The first line treatment for malaria in the public health system is artemether /lumefantrine in each district. Cases of uncomplicated malaria are treated at one of the health centres in the district and in Bougouni some cases are treated in the community by trained community health workers. Cases of severe malaria are managed in the district hospital. During the SMC + AZ trial the incidence of clinically suspected meningitis in children aged 3 - 59 months in Bougouni was approximately 0.11 per 1,000 per year and that of cerebral malaria 0.88 per 1,000 per year.

During 2014-2017, Houndé and Bougouni districts were the sites of a trial, involving approximately 20,000 children aged 3-59 months, which evaluated the impact of adding azithromycin to the SP +

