Children with a history of an adverse reaction to SP or AQ, known to have a serious underlying illness including known HIV infection not well controlled by treatment, having severe malnutrition (z scores < 3 SD) or known to have previously received a malaria vaccine were excluded from the trial.

Children known to have received SMC during the year prior to enrolment (either through the previous study in these districts (AZ-SMC, [NCT02211729](#)), or from the national programme) were not excluded from this study.

The list of eligible children in each country was sorted by location (village), age in months, gender and prior receipt of SMC, before assigning randomisation codes in permuted blocks of 9, to give an implicit stratification on these factors.

Sample size and Study Design

Based on the calculations described below, the trial aimed to recruit approximately 3,000 children in Burkina Faso and 3,000 in Mali (total 6,000) who would be followed for three years. A low dropout rate of around 5% per year (15% overall) was anticipated based on findings from the previous trial conducted in the same study areas.

In Burkina Faso and Mali, 2777 and 3143 children, respectively, received the first dose of study vaccine.

Superiority comparison: The trial was designed to compare the two interventions combined with either used alone. The study is powered to i) assess the statistical evidence against the null hypothesis of no difference between the combined group and either the SMC alone or RTS,S alone group, and ii) estimate the efficacy of the combined group relative to the single intervention groups with a relatively high degree of precision. This latter aspect is important because if the combined intervention is to be used in practice, it is necessary to show that adding RTS,S/AS01 to SMC has a clinically significant benefit.

After two years of follow-up, incidence of clinical malaria, as defined below, was approximately 200 cases per 1000 child-years at risk. With approximately 2000 individuals in each arm, if the

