Hypothesis testing will follow the closed testing procedure, whereby there is initially a test of the null hypothesis that the incidence in the three groups is the same. If this is rejected at the 5% level, pairwise comparisons will be done also using a 5% significance level. Pairwise comparisons can be considered statistically significant only if the overall null hypothesis is rejected.

For the non-inferiority comparison described above, we will calculate two-sided 95% confidence intervals, equivalent to the use of a one-sided significance level of 2.5%, as is recommended (4). To illustrate the level of confidence with which non-inferiority can be declared, we will plot the point estimate for the hazard ratio with two-sided 90, 95 and 99% confidence intervals, and the non-inferiority margin.

Database and randomisation codes

Data have been collected using electronic case record forms (eCRF) developed using Open Data Kit (ODK) software. Tablet PCs are used to document all intervention contacts and all active surveillance contacts such as the weekly and cross-sectional surveys. For passive case detection, tablet PCs loaded with eCRFs are available at all study health centres that provide treatment. Data are transferred from the eCRFs held in the research sites to a central data management

team. Automatic checks are performed on clinical and laboratory forms to ensure that they are complete and contain valid responses prior to transferring data. Further checking and cleaning of the data (including checks for duplicate entries, consistency and range checks of variables) is then carried out by the data management teams in Burkina Faso and Mali using MS Access.

The consistency of merges between different database tables will be undertaken blind to randomisation group. The analysis databases and analysis programmes (written as Stata do files) will also be prepared for the primary and key secondary analyses before the randomisation code is broken.

A final version of the database for analysis, following approval by the Data and Safety Monitoring Board (DSMB) will be burned to CD and a copy sent to the chair of the DSMB for archiving.

The randomisation codes will only be released when the final database is ready and authorisation is given by the DSMB.

All data used for analysis of the main trial report will be annotated and archived. Stata code used for the analyses will also be archived.

Primary Endpoint

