The prevalence ratio of secondary endpoints measured at the weekly survey (aggregated into three-month periods), and at end of season surveys (including *P. falciparum* parasitaemia, anaemia, etc) will be estimated using Poisson regression, with a robust standard error for the individual, as described in Zou, 2004 (10).

Linear regression models will be used to compare mean haemoglobin concentration between the groups.

Arithmetic mean parasite densities (including in the calculation samples which are parasite negatives, as having density of zero), will be compared between arms using Poisson regression with a robust standard error.

Covariates

All analyses (primary outcomes and secondary outcomes) will adjust for study country only (Burkina Faso or Mali).

For the primary outcome, we will also build a model adjusting for the following potential confounders:

- Age at enrolment
- Child's Sex
- Bednet use at baseline

Pre-specified subgroup analyses, interactions and exploratory analyses

As described above, the primary analysis will be pooled across the two study centres, stratified by (i.e. adjusted for) country. Efficacy (ratio and difference) measures will be presented for both sites combined. Investigation of any differences in intervention effects between the centres (formally, evidence for an interaction between intervention group and study centre) is pre-specified due to possible differences in performance of these interventions under different malaria transmission intensity. All outcomes will, therefore, also be tabulated by centre, and site specific efficacy estimates will be presented.

Investigation of differences between study groups in successive years of the study is also pre-specified, because it is possible that the efficacy of RTS,S/AS01 booster doses is different to the primary series. This will be assessed by exploring evidence for an interaction between intervention group and study year (2017-18, 2018-19, 2019-20).

Finally, evidence for effect modification by age at enrolment will be explored. It is possible that vaccination will perform differently according to the extent of prior exposure to malaria. Of particular interest are participants who were young infants at the time of the first vaccination in 2017, as they may have had no exposure to malaria prior to enrolment in the trial.

Pre-specified Secondary analyses

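### Robust-SE Cox and Poisson models for sparse secondary outcomes give an invalid interval and P<0.001 when one compared arm has no events, and the SAP has no rule for that case

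*Combined protocol and SAP*

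**What the plan says.** All references are to SAP revision 1 unless stated.

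- **Passively detected outcomes.** Statistical methods, Secondary endpoints, prescribes "estimating the hazard ratio using Cox regression with a robust standard error". This one method covers malaria admissions and their severe-malaria subtypes (2.2.3), transfusions (2.2.4), all-cause deaths (2.2.5) and malaria deaths (2.2.7).
- **Survey outcomes.** The prevalence ratio "will be estimated using Poisson regression, with a robust standard error for the individual". These outcomes include severe anaemia (2.4.10) and, in the weekly surveys grouped into three-month periods, high-density parasitaemia (2.3.2).
- **Splits.** The subgroup section says: "All outcomes will, therefore, also be tabulated by centre, and site specific efficacy estimates will be presented". The layouts of Tables 1 and 2, by country and by study year, are reused for the passively detected secondary outcomes.
- **Testing.** Sample size and Study Design sets a closed procedure. A three-group test comes first and, if it rejects, "pairwise comparisons will be done also using a 5% significance level". The tables have a homogeneity column, but the statistic behind it is not named.
- **Zero counts.** The only outcome handled differently is meningitis, "with no events up to the 30th November 2019", for which just a confidence interval for the rate is planned. There is no minimum event count, exact test, score or profile-likelihood interval, or penalised fit for any other outcome.

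**The concern.** A Wald test divides an estimate by its standard error. With an empty arm the maximum likelihood estimate of the log ratio does not exist, and software stops at an arbitrary large value. A model-based standard error diverges with it, so the output is visibly uninformative. A sandwich standard error does not diverge, so the output looks like overwhelming evidence. The outcomes most likely to have an empty arm are the severe and safety outcomes, particularly within one centre or year. A single event in one arm and none in another would then be printed with a minute P value and an interval that excludes every plausible ratio.

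**Working it through.** The documents give no figure for this point, so there is none to reproduce.

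**1. Why the robust standard error stays finite.** Take a Poisson model with n children per arm, d events in one arm and 0 in the other. The sandwich variance of the log ratio is a sum over the two arms:
- arm with events: (1 - d/n)/d
- empty arm with fitted mean m per child: n·m²/(n·m)² = 1/n, whatever m is.

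With n = 1,000:
- d = 1: 0.999 + 0.001 = 1.000, SE 1.00
- d = 3: 0.3323 + 0.001 = 0.3333, SE 0.577.

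The model-based variance is 1/d + 1/(n·m), which goes to infinity as m goes to 0. For the Cox model the sandwich variance likewise tends to 1/d.

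**2. Fitted results.**

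| Model, events | log ratio or HR | robust SE | robust P | exact P |
|---|---|---|---|---|
| Poisson, 0 v 1 (1,000 per arm) | -20.4 | 1.00 | about 1e-92 | 1 |
| Poisson, 0 v 3 (1,000 per arm) | -21.4 | 0.577 | about 1e-300 | 0.25 |
| Cox, 0 v 1 (1,973 per arm) | HR 1.7e-9 (2.4e-10 to 1.2e-8) | 1.00 | 1e-90 | 1 |
| Cox, 0 v 3 (1,973 per arm) | not shown | 0.58 | 8e-268 | 0.25 |

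Model-based P for the two Poisson rows is 0.999. The Cox fits used constructed data with delayed entry and 15% loss. A three-arm Cox fit with a country term and events 1/1/0 gave the same artefact. At a loose convergence tolerance (1e-5) the log HR was still about -10.7 with P = 3e-26, so the stopping rule is not the cause. Once every arm has an event (2/1/1, 5/5/5), robust and model-based standard errors agree.

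**3. How often an empty arm would occur.** Inputs:
- Children: "In Burkina Faso and Mali, 2777 and 3143 children, respectively, received the first dose of study vaccine".
- Rate: protocol section 3 (Study area) reports for Bougouni "that of cerebral malaria 0.88 per 1,000 per year". It comes from an earlier trial in ages 3-59 months; applying it to both centres is an assumption.
- Follow-up: about 2.9 years from vaccination to 31 March 2020, taken as 2.7 years per child after losses (assumption).

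Expected cases per arm:
- Mali: 3143/3 × 2.7 × 0.00088 = 2.49
- Burkina Faso: 2777/3 × 2.7 × 0.00088 = 2.20
- Pooled: 5920/3 × 2.7 × 0.00088 = 4.69.

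With equal true rates and mean μ per arm, P(one of a pair is zero, the other is not) = 2e^(-μ)(1 - e^(-μ)):
- Mali: 15.2%
- Burkina Faso: 19.7%
- Pooled: 1.8%
- One study year, both centres (μ = 4.69/3 = 1.56): 33%.

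The documents give no rates for malaria deaths, transfusions or Hb <5 g/dL. For an assumed μ of 0.5, 1 and 3 the chance is 48%, 47% and 9%.

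**4. Effect of the closed-testing gate.** I enumerated three equal Poisson arms and required both the zero-versus-some pattern in a given pair and rejection of homogeneity at 5% (2 df):

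| μ | pattern alone | with score gate | with likelihood-ratio gate |
|---|---|---|---|
| 2.20 | 19.7% | 2.3% | 3.9% |
| 2.49 | 15.2% | 2.1% | 4.0% |
| 1.00 | 46.5% | 2.4% | 2.5% |

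If the global test is itself robust Wald, it fails in the same way (P = 3e-168 for events 1/1/0) and gives no protection.

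**5. What an exact method gives for 0 versus d, equal person-time.** P = min(1, 2 × 0.5^d); upper limit of the ratio = 0.025^(-1/d) - 1. Results: d = 1, P = 1, limit 39; d = 3, P = 0.25, limit 2.4; d = 5, P = 0.063, limit 1.09; d = 6, P = 0.031, limit 0.85.

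**The case against.** The strongest reply is the closed procedure. A pairwise result cannot be called significant unless homogeneity is rejected, and with an ordinary score or likelihood-ratio global test the error stays below 5%. This stands. A reader might take the 15-20% as a false-significance rate, but the documents support that only if the unnamed homogeneity test is robust Wald. The gate does not repair the pairwise interval and P value, which are printed either way.

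Pooled results, which are the main analysis, are scarcely affected for cerebral malaria. This also stands; the exposure is in the centre and year splits and in rarer outcomes whose rates are not given.

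The cerebral malaria safety analysis specifies Cox regression without stating the standard error, and under 2.2.3 the subtype is an additional analysis. That is true, but 2.2.3 still falls under the general rule. A reader might also infer that a real difference such as 0 versus 12 would be missed. That needs a model-based standard error, which the general rule does not prescribe, and far more events than the protocol's rate suggests.

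An analyst would notice a hazard ratio near 1e-9 beside a zero count. Probably so, but the replacement would then be chosen after seeing the counts. The SAP wants programs for primary and key secondary analyses ready before the code is broken.

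Two technical limits apply. On the log scale the 0-versus-1 interval is not narrow: its limits differ about 50-fold. The fits were not run in Stata, which the trial uses, and with an empty reference arm some less stable computations returned missing or inflated standard errors.

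**Conclusion.** The concern holds in bounded form. For a pair with events in only one arm, the prescribed models return an invalid interval and pairwise P<0.001 regardless of how few events there are. If both compared arms are empty and a third is not, the Cox ratio is near 1 with a falsely tight interval (robust SE about 0.05 in the fit with one event in the third arm).

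Under the stated assumptions on rate and follow-up, the pattern would arise by chance in about 15-20% of within-centre pairs for cerebral malaria and about 2% of pooled pairs. The share formally declared significant is about 2-4% with a score or likelihood-ratio gate, and up to 15-20% with a robust Wald gate.

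The documents do not support extending this to the primary endpoint, where incidence is about 200 per 1,000 child-years. Nor do they support treating sparse but non-empty arms as failing in the same way.

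**What to change.** Add to Secondary endpoints: when any compared arm has zero events (overall, by centre, by year or in a survey window), the robust Wald ratio, interval and P value are replaced by counts, rates and an exact interval and P value.

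- **Passively detected outcomes:** exact conditional Poisson on children with at least one event, because admissions and transfusions can recur in a child and the exact method assumes independence.
- **Prevalences:** Fisher or exact binomial.
- **Pooled results:** stratified by country.
- **Homogeneity column:** name a score or likelihood-ratio test.
- **Cerebral malaria safety analysis:** apply the same rule.
- **Sex-by-vaccine mortality interaction:** use a likelihood-ratio or exact test in place of the Wald test if a cell is empty.

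Extending the rule to a low total, such as fewer than about 10 events in the two arms, is optional.

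The cost is one paragraph and a few lines of code. Exact results are conservative: 0 versus 5 gives P = 0.063.
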